Subjects receiving placebo for ixekizumab 20 mg or 40 mg will receive 1 SC injection of placebo at Week 0 (Visit 2) and 1 SC injection of placebo Q4W at Weeks 4 and 8. Subjects receiving placebo for ixekizumab 80 mg will receive 2 SC injections of placebo at Week 0 (Visit 2) and 1 SC injection of placebo Q4W at Weeks 4 and 8.
Group 2: Subjects randomized to etanercept will receive etanercept every week (Q1W) at Week 0 through Week 11. After training by the clinical staff, injections of etanercept will be self-administered by the subject or caregiver, as described in Section 7.1.
- u All subjects receiving IP must enter into the Post-Treatment Follow-Up Period (Period 5) and complete through Visit 802. Subjects may be followed beyond Visit 802 for continued monitoring of their neutrophil counts. If a subject discontinues IP early, the subject will complete the ETV and then enter the Post-Treatment Follow-Up Period (Period 5).
- v This visit will only occur if a subject's neutrophil counts have not returned to the defined criteria.
- w **Group 1:** All subjects from non-EU countries and nonresponders from EU countries will receive 1 SC injection of ixekizumab Q4W.
Group 2: Responders from EU countries will be rerandomized to either ixekizumab or placebo. Subjects will receive 1 SC injection Q4W. Subjects on placebo will receive ixekizumab upon disease relapse to psoriasis (sPGA \geq 2).

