5.1. Summary of Study Design

Study I1F-MC-RHCD (RHCD) is a Phase 3, multicenter, double-blind, randomized, placebo-controlled study examining the effects of ixekizumab versus placebo in subjects from 6 to <18 years of age with moderate-to-severe plaque psoriasis (Ps) (Psoriasis Area and Severity Index [PASI] score ≥ 12 , static Physician's Global Assessment [sPGA] ≥ 3 , and body surface area [BSA] $\geq 10\%$ at screening and baseline). Protocol Addendum I1F-MC-RHCD(1) specifies the pharmacokinetics (PK) collection schedule and how the data from the approximately 24 subjects participating in the PK addendum will be used. Protocol Addendum I1F-MC-RHCD(2) specifies the details for the active-controlled (etanercept) portion of the study design, as well as a double-blind, randomized withdrawal period for subjects from European Union (EU) countries.

The study consists of 5 periods:

- **Period 1: Screening Period** (Visit 1) will assess subject eligibility and will occur approximately 7 to 30 days before Period 2 (baseline; Week 0; Visit 2).
- **Period 2: Double-Blind Treatment Period** (Induction Period) will occur from Week 0 (baseline; Visit 2) to Week 12 (Visit 7), comparing ixekizumab with placebo in a double-blind fashion. The dose of ixekizumab will not be adjusted during this period. Protocol Addendum I1F-MC-RHCD(2) describes etanercept as a reference control group for countries where etanercept is approved for treatment of chronic severe Ps in children and adolescents from the age of 6 years who are inadequately controlled by, or are intolerant to, other systemic therapies or phototherapies.
- **Period 3: 48-Week, Open-Label Maintenance Period** will occur from Week 12 (Visit 7) to Week 60 (Visit 19). Subjects randomized to the ixekizumab group during Period 2 will maintain the dose received during the previous period. Subjects randomized to placebo during Period 2 will receive ixekizumab at doses of 20, 40, or 80 mg, based on weight. As part of Protocol Addendum I1F-MC-RHCD(2), subjects randomized to etanercept during the Double-Blind Treatment Period will begin treatment with ixekizumab after an 8-week washout period (to avoid, for safety reasons, increased risk with concurrent etanercept and ixekizumab exposures). If a subject changes weight category following the Double-Blind Treatment Period, the ixekizumab dose associated with that weight will be administered. This may happen at any time during the Maintenance Period.

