5.2.2. Protocol Addendum RHCD(2)

During the Double-Blind Treatment Period, approximately 75 subjects with severe Ps from etanercept-approved countries will be randomized to ixekizumab (30 subjects), etanercept (30 subjects), and placebo (15 subjects) with 2:2:1 ratio.

Study RHCD(2) will have approximately 85% power to test the superiority of ixekizumab to etanercept for sPGA (0,1) and at least a 75% improvement from baseline in PASI score (PASI 75) at Week 12, based on the 2-sided Fisher's exact test at significance level of 0.05. The study will have approximately 45% power to test the superiority of etanercept to placebo for PASI 75 at Week 12, based on the 2-sided Fisher's exact test at significance level of 0.05. The following assumptions were used for the power calculations for both sPGA (0,1) and PASI 75 response rates, based on ixekizumab clinical studies in adult subjects with moderate-to-severe Ps efficacy data (Griffiths et al. 2015; Gordon et al. 2016): 80% responders for ixekizumab, 40% responders for etanercept, and 10% for placebo.

During the Double-Blind, Randomized Withdrawal Period (Period 4), approximately 40 subjects from EU countries will be re-randomized to ixekizumab (20 subjects) and placebo (20 subjects) with a 1:1 ratio. The response criterion for re-randomization is sPGA (0,1) at Week 60. The study will have approximately 95% power to test the superiority of ixekizumab to placebo in time to relapse, based on the 2-sided log-rank test at significance level of 0.05. The following assumptions were used for the power calculations: 20% relapse for ixekizumab; and 85% relapse for placebo. Relapse rates were estimated, based on ixekizumab clinical studies in adult subjects with moderate-to-severe Ps efficacy data (Griffiths et al. 2015; Gordon et al. 2016).

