Ixekizumab Efficacy Secondary Population	Combined Treatment Periods 3 and 4	Patients initially randomized to placebo or etanercept who switch to ixekizumab during Period 3. The following data is not included in this analysis population: (1) patients initially randomized ixekizumab; (2) Period 4 data for patients re-randomized to placebo at Week 60.
All Ixekizumab Safety Population	Combined Treatment Periods.	All subjects who have at least 1 dose of ixekizumab, including patients in main protocol and Protocol Addendum(2).
Follow-Up Population	Post-Treatment Follow-Up Period (Period 5)	Safety analyses for Post-Treatment Follow-Up Period will be conducted on the Follow-Up Population, defined as all randomized subjects who received at least 1 dose of study treatment and have entered the Post-Treatment Follow-Up Period. Patients will be analyzed according to the last treatment they received before entering Period 5.

Abbreviations: EU = European Union.

Table RHCD.6.2. Treatment Groups and Comparisons for Each Study Period and Analysis Population

Study Period	Analysis Population	Treatment Group	Abbreviation	Comparison
Double-Blind Treatment Period (Period 2)	Intent-to-Treat Population; Per-Protocol Set; Safety Population	Ixekizumab Q4W	IXEQ4W	IXEQ4W vs. PBO
		Etanercept Q1W	ETN	IXEQ4W vs. ETN
		Placebo Q4W	PBO	ETN vs. PBO
Randomized-Withdrawal Period (Period 4)	Double-Blind, Randomized Withdrawal Period Population	Ixekizumab Q4W	IXEQ4W	IXEQ4W vs. PBO
		Placebo Q4W	PBO	
Combined Treatment Periods (Period 2, 3, 4)	Ixekizumab Efficacy Primary Population, All Ixekizumab Safety Population	Ixekizumab Q4W	IXEQ4W	NA
Combined Treatment Periods 3 and 4	Ixekizumab Secondary Primary Population	Placebo Q4W/ixekizumab Q4W	PBO/IXE	NA
		Etanercept Q4W/ixekizumab Q4W	ETN/IXE	
Post-Treatment Follow-Up Period (Period 5)	Follow-Up Population	Ixekizumab Q4W	IXEQ4W	No comparison
		Etanercept	ETN	
		Placebo Q4W	PBO	

Abbreviations: ETN = etanercept; IXE = ixekizumab; NA = not applicable; PBO = placebo; Q1W = every week; Q4W = every 4 weeks; vs. = versus.

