6.14.4.2. Neutrophil Follow-Up

Neutrophil counts will be followed throughout the study. Patients will continue in Period 5 until their neutrophil counts have recovered.

The neutrophil follow-up analysis will be conducted on the Neutrophil Follow-Up Population defined as patients who have an absolute neutrophil count <1500 cells/ μ L (SI units: <1.5 $\times 10^9$ /L) at the last scheduled visit or early termination visit prior to entering the Post-Treatment Follow-Up Period (Period 5) and less than the patient's baseline absolute neutrophil count (that is, prior to first injection at Week 0). These patients are monitored during the Period 5 until neutrophil recovery.

Neutrophil clinical recovery is defined as an absolute neutrophil count \geq 1500 cells/ μ L (SI units: \geq 1.5 $\times 10^9$ /L) or greater than or equal to a patient's minimum absolute neutrophil count prior to first study drug injection at Week 0.

If a patient's neutrophil count has not recovered, within 12 weeks after entering the follow-up period (Visit 802), the patient will return for Visit 803 (12 weeks after Visit 802). Additional visits may be required for appropriate patient management depending upon the degree of neutropenia. If at Visit 802, a patient's has met the criteria for neutrophil recovery, the patient's participation in the study will be considered complete, unless the investigator deems additional follow-up may be necessary.

The number and percentage of patients achieving neutrophil clinical recovery will be presented by dosing regimen and week interval for Neutrophil Follow-Up Population for Post-Treatment Follow-Up Period (Period 5). The number and percentage of patients with an absolute neutrophil cell count that is at least 25%, 50%, 75%, or 100% of the patient's baseline absolute neutrophil count (that is, prior to first injection at Week 0), irrespective of absolute neutrophil minimum, will be included in the summary.

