- TE-ADA negative:** A patient who is evaluable for TE-ADA and is not either TE-ADA positive or TE-ADA inconclusive.

Figure RHCD.6.3 illustrates the relationship of some of these terms.

Abbreviation: ADA = anti-drug antibody.

Figure RHCD.6.3. Relationship of terms for clinical interpretation of assay results for evaluable patients.

- **Incidence of TE-ADA:** Patients with TE-ADA as a proportion of the evaluable patient population during the treatment period. This excludes unevaluable patients.
- **Follow-up-emergent ADA:** ADA is first detected during the follow-up period, after study drug administration is discontinued. This category includes patients negative at baseline who increased to $\geq 1:10$ titer (4-fold increase/ 2 dilutions) after baseline in the follow-up period or patients ADA positive at baseline and increased at least 4-fold (2 dilutions) over baseline for the first time in the follow-up period.
- **Incidence of follow-up emergent ADA:** Patients with follow-up-emergent ADA as a proportion of the follow-up evaluable patient population. This excludes unevaluable patients.

All ADA positive samples will be evaluated for NAb. Definitions for NAb patient status will be defined as follows:

- **NAb-positive:** A patient where a NAb positive result is detected for ≥ 1 TE-ADA positive samples.
- **NAb-inconclusive:** A patient without a NAb positive sample and with at least 1 sample for which drug levels may interfere with the NAb assay.
- **NAb-negative:** A patient who is evaluable for NAb and is not either NAb positive or NAb inconclusive.

A flow chart that reflects the connection between the analytical test results and the clinical interpretation based on the definitions is shown in [Figure RHCD.6.4](#).

[figure not shown]

Figure RHCD.6.4. Flow chart of ADA assessment with clinical interpretation of the various result possibilities.

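### The Period 5 placebo group pools withdrawal-placebo subjects who were not retreated, after up to 40, 48 or 60 weeks of ixekizumab, with Period 2 placebo dropouts who never received it

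*SAP*

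**What the plan says.** SAP Section 6.1.1, Table RHCD.6.1, describes the Follow-Up Population as "defined as all randomized subjects who received at least 1 dose of study treatment and have entered the Post-Treatment Follow-Up Period". The grouping rule follows: "Patients will be analyzed according to the last treatment they received before entering Period 5". Table RHCD.6.2 lists three Period 5 groups (ixekizumab, etanercept, placebo) and enters "No comparison" for them.

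Three other parts of the plan decide who can reach Period 5 with placebo as last treatment:

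- **Early stoppers enter Period 5.** In the protocol addendum, Attachment 1 (Schedule of Activities footnotes), a subject who stops investigational product early completes the early termination visit and then enters Period 5.
- **Everyone who continues past Period 2 goes to ixekizumab.** SAP Section 5.1: "Subjects randomized to placebo during Period 2 will receive ixekizumab at doses of 20, 40, or 80 mg, based on weight". Figure RHCD.5.2, footnote g, starts former etanercept subjects at Week 20.
- **Some return to placebo.** SAP Section 5.3.2 re-randomizes EU responders 1:1 to ixekizumab or placebo at Week 60, and gives open-label ixekizumab to those who relapse.

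The sample-size assumptions for that withdrawal period (SAP Section 5.2.2) are 20 subjects per arm and "20% relapse for ixekizumab; and 85% relapse for placebo".

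**The concern.** A Period 5 column headed placebo will normally be read as subjects without exposure to the test drug. Under the last-treatment rule it also holds children with long prior ixekizumab exposure, and nothing in the SAP separates the two for Period 5.

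The summaries at stake are:

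- follow-up-emergent adverse events (Section 6.14.2);
- cytopenia and hepatic laboratory results, the two special topics kept for Period 5 (Section 6.14.3.1);
- follow-up-emergent laboratory abnormalities and cell-count shifts (Sections 6.14.4 and 6.14.4.1);
- neutrophil recovery, which "will be presented by dosing regimen and week interval for Neutrophil Follow-Up Population" (Section 6.14.4.2);
- follow-up-emergent anti-drug antibodies, to the extent that they are shown by group.

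Prior exposure matters most for the last. An antibody to ixekizumab means one thing in a child never given the drug and another in a child given it for most of a year.

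Elsewhere the SAP keeps treatment sequence visible. Table RHCD.6.2 has PBO/IXE and ETN/IXE rows for Periods 3 and 4. The two ixekizumab efficacy populations remove subjects re-randomized to placebo, or their Period 4 data. Table RHCD.6.10 lists each sequence that ends in withdrawal placebo. The distinction is lost only in Period 5.

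**Working it through.** **1. Routes to placebo as last treatment.** Subjects who continue past Week 12 move to ixekizumab, so only two routes remain:

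- (a) stopping on placebo in Period 2, before any ixekizumab;
- (b) re-randomization to placebo at Week 60 with no ixekizumab afterwards.

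Table RHCD.6.2 puts (a) and (b) in the same row.

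**2. Ixekizumab time before Week 60** = 60 minus the starting week.

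| Period 2 arm | Ixekizumab starts | Weeks to Week 60 |
|---|---|---|
| Ixekizumab | Week 0 | 60 |
| Placebo | Week 12 | 60 − 12 = 48 |
| Etanercept | Week 20 | 60 − 20 = 40 |

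**3. Check on the withdrawal inputs.** The SAP's power of about 95% uses the same 20 per arm and the same relapse rates.

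- Under exponential times, hazard ratio = ln(0.80)/ln(0.15) = 0.118.
- Expected relapses = 20 × (0.20 + 0.85) = 21.
- Freedman's formula: power = Φ(√21 × (1 − 0.118)/(1 + 0.118) − 1.96) = 0.951.

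The stated figure is reproduced. (Schoenfeld's formula gives 0.998.) This only confirms how the inputs were used; the point does not depend on it.

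**4. Size of group (b).** I take the relapse rates to apply over Period 4 and every relapse to lead to retreatment.

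- Not retreated: 20 × (1 − 0.85) = 3 (binomial 95% range 0 to 6).
- Retreated, hence grouped as ixekizumab: 20 × 0.85 = 17.
- If relapse were 70%, 6 would not be retreated; if 95%, 1.

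Subjects who leave Period 4 while on placebo, before any retreatment, add to group (b). The documents give no rate for this.

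**5. Size of group (a), and the mix.** The documents give no Period 2 dropout rate. I assume 2% to 15% of the 55 placebo subjects in SAP Section 5.2.1, which is 1.1 to 8.25 subjects. Share with prior ixekizumab = b/(a + b).

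| Assumed Period 2 placebo dropout | a | b = 6 (70% relapse) | b = 3 (85% relapse) | b = 1 (95% relapse) |
|---|---|---|---|---|
| 2% | 1.1 | 85% | 73% | 48% |
| 5% | 2.75 | 69% | 52% | 27% |
| 10% | 5.5 | 52% | 35% | 15% |
| 15% | 8.25 | 42% | 27% | 11% |

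At 85% relapse the column would hold about 4 to 11 subjects (3 + 1.1 to 3 + 8.25).

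**The case against.** The case for leaving the rule alone has real force.

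- **Few subjects.** A reader might infer that the whole withdrawal-placebo arm is reported as placebo. It is not. Subjects who relapse receive ixekizumab, so the rule puts about 17 of 20 in the ixekizumab group.
- **Not the only unexposed group.** A reader might infer that Period 5 loses its one ixekizumab-naive reference. Subjects whose last treatment was etanercept have not had ixekizumab either. Placebo is the only *placebo* reference, no more.
- **Late effects are not shown to be hidden.** A withdrawal-placebo subject who completes Week 108 has been off ixekizumab for about 48 weeks. Effects of withdrawal would appear mostly in Period 4, where these subjects are summarized against ixekizumab. All adverse events are also listed by patient. For such completers placebo is an accurate description of the last treatment. The time off drug is shorter only for those who leave Period 4 early.
- **No formal comparison.** Table RHCD.6.2 specifies none. This holds only in part. Section 6.14.4 plans Fisher's exact tests between treatment groups for laboratory abnormalities, names follow-up-emergent ones among them, and covers each safety population. Section 6.14.4.1 calls the follow-up set a safety population.
- **Antibody and neutrophil tables may not use this row.** Incidence of follow-up-emergent antibodies is defined as "Patients with follow-up-emergent ADA as a proportion of the follow-up evaluable patient population", with no split by group stated. Neutrophil recovery is by dosing regimen, a term not tied to the rows of Table RHCD.6.2, and in a subset that few of these subjects may enter. Both are affected only if shown by these groups.

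What survives is the labelling. The rule is prespecified and clear, yet it puts subjects with and without prior ixekizumab under one heading.

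**Conclusion.** The point stands as a labelling defect of limited size. Subjects re-randomized to placebo and not retreated (about 3 of 20 at the SAP's 85% relapse, plus early stoppers on placebo) are pooled in Period 5 with Period 2 placebo dropouts who never had ixekizumab. The 40, 48 and 60 weeks of prior exposure follow directly from the schedule.

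The share of the column that is ixekizumab-experienced should not be quoted as a finding. It runs from 27% to 73% at 85% relapse, and more widely otherwise, because the Period 2 dropout rate is my assumption and the numerator is itself uncertain. What can be said is that the column is likely to be small and that its composition cannot be read from its label. With 4 to 11 subjects, a single event would read as 25% to 9% on placebo (1/4 to 1/11).

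No primary or gated result is affected, and the Period 4 withdrawal analysis is untouched.

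**What to change.** In Table RHCD.6.2, replace the Period 5 placebo row with two rows:

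- *PBO, no prior ixekizumab*
- *IXE/PBO (randomized withdrawal, not retreated)*

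Use the same split wherever Period 5 neutrophil recovery and follow-up-emergent antibodies are shown by group, and state in Sections 6.14.4.2 and 6.14.11.2.1 which groups those summaries use. Also reconcile the absence of a Period 5 comparison in Table RHCD.6.2 with the Fisher's exact tests in Section 6.14.4.

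The cost is one extra column built from treatment history already collected. Conduct, sample size and alpha do not change, and the final database lock comes after Period 5 (Section 6.17). The downside is sparse columns: about 3 subjects in one, and perhaps 1 to 8 in the other on the dropout range assumed here. The second row is also a selected group, largely subjects who did not relapse, so the two rows should be described and not tested against each other.

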6.1.2. Baseline Definition

For the Double-Blind Treatment Period (Period 2; ITT Populations), as well as the Combined Treatment Periods (Ixekizumab Efficacy Primary Population and Ixekizumab Efficacy Secondary Population), the baseline for efficacy and health-outcome analyses will be defined as the last available value before the first injection. In most cases, this will be the measure recorded at Week 0 (Visit 2). For efficacy and health-outcome measures, if the patient does not take any injection, the last available value on or prior to randomization date will be used.

Unless, otherwise, specified, baseline for safety during Period 2 is defined as follows:
for categorical data, baseline includes all available values before the first injection at Week 0;
for continuous data, baseline is the last available value before the first injection at Week 0.

Protocol Addendum I1F-MC-RHCD(2), for the Double-Blind Randomized Withdrawal Period in Subjects in EU Countries, the baseline for efficacy and health-outcome analyses will be defined as the measure recorded at Week 0 (Visit 2). For safety analysis, the baseline is defined as the last available values before the re-randomization (Week 60).

For safety analysis during the Combined Treatment Periods (Periods 2, 3, and 4; Ixekizumab Safety Population): patients who were initially randomized to ixekizumab at Week 0, baseline period is defined as the time from Visit 1 to the date/time of the first injection. For patients initially randomized to placebo or etanercept, baseline is defined as last available value prior to first dose of ixekizumab. For patients who get re-randomized to placebo during the Double-Blind Randomized Withdrawal Period (Protocol Addendum RHCD[2]), they may enter the rescue arm on ixekizumab after relapse. The baseline for this second ixekizumab exposure period will be the last nonmissing value during the placebo exposure period and prior to the ixekizumab injection. For patients who had 2 separate ixekizumab exposures, the baseline for the shift tables and standardized growth analyses in both exposure periods will be defined as the baseline for the first ixekizumab exposure period.

For the Post-Treatment Follow-Up Period (Period 5), the baseline is defined as the last nonmissing assessment on or prior to entering Period 5, that is, on or prior to Week 108, or ETV.

Change from baseline will be calculated as the visit value of interest minus the baseline value. If all baseline values are missing for a particular variable, then the change from baseline and the percent improvement from baseline will not be calculated.

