6.1.3. Analysis Methods

6.1.3.1. Double-Blind Treatment Period (Period 2): Main Protocol

The primary analysis method for categorical data for treatment group comparisons will be Fisher's exact test. The difference of the proportions and the 95% CI of the difference will be included.

Secondary analyses for the primary efficacy measures, PASI 75 and sPGA(0,1), and other categorical efficacy and health outcome measures, will be conducted using a logistic regression analysis with treatment group, region, baseline sPGA score (severity of Ps), and baseline weight category (<25 kg, ≥25 to ≤50 kg, or >50 kg) as factors. The odds ratio and the corresponding 95% CI will be reported.

The analyses for the continuous efficacy and health-outcome variables will be made using analysis of covariance (ANCOVA) and mixed model for repeated measures (MMRM) analysis. The ANCOVA model includes treatment group, region, baseline sPGA score, baseline weight category, and baseline value. Type III sums of squares for the least-squares means will be used for the statistical comparison; the 95% CI will be reported.

When the MMRM is used, the model will include treatment, region, baseline sPGA score, baseline weight category, baseline value, visit, treatment-by-visit, and baseline-by-visit interactions as fixed factors. The covariance structure to model the within-subject errors will be unstructured. The Kenward-Roger method will be used to estimate the denominator degrees of freedom. Type III tests for the least-squares means will be used for the statistical comparison; the 95% CI will be reported. Treatment comparisons at Week 12 and all other postbaseline visits will be reported.

If the unstructured covariance matrix results in a lack of convergence, the heterogeneous Toeplitz covariance structure, followed by the heterogeneous autoregressive covariance structure, followed by the compound symmetry will be used. This order is specified according to a decreasing number of covariance parameters in the structure. The sandwich estimator (Diggle et al. 1994) for the covariance estimation will be used by specifying the EMPIRICAL option in SAS PROC MIXED. When sandwich estimation is used, the Kenward-Roger approximation for denominator degrees of freedom cannot be used. Instead, the DDFM= BETWITHIN option will be used to estimate denominator degrees of freedom.

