6.1.3.4. Double-Blind Randomized Withdrawal Period (Period 4)

The time to relapse (loss of response; sPGA ≥ 2) during Double-Blind, Randomized Withdrawal Period (Period 4) is defined as:

Time to relapse (days)

$$= \text{date of first sPGA} \geq 2 \text{ during Period 4} - \text{date of Week 60 rerandomization} + 1$$

If a patient has not experienced relapse by completion or early discontinuation of Period 4, the patient will be censored at the date of his/her last visit during Period 4.

The number of patients at risk and experiencing a relapse event by each scheduled visit during Period 4 will be presented by treatment group. The Kaplan-Meier estimate of the proportion of patients relapsing will be presented for each visit. Treatment group comparisons will be performed using the log-rank test. For each treatment group, a Kaplan-Meier plot of the time to relapse will be provided.

The analysis method for categorical data for treatment group comparisons will be Fisher's exact test. The difference of the proportions and the 95% CI of the difference will be included.

Fisher's exact test will be used for all AEs, baseline characteristics, discontinuation, and other categorical safety data. The continuous baseline characteristics will be analyzed using an ANOVA model with treatment as a factor. Continuous vital sign data and laboratory values will be analyzed by an ANCOVA with treatment and baseline value in the model.

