 & = \frac{\textit{Date of informed consent} - \textit{Date of psoriasis onset}}{365.25}
 \end{aligned}$$

- Age at psoriasis diagnosis (in years)
- Duration of psoriasis diagnosis (in years): will be calculated using the date of psoriasis diagnosis (as recorded on the Prespecified Medical History – Psoriasis eCRF page) as follows:

$$\begin{aligned}
 & \textit{Duration of psoriasis diagnosis (years)} \\
 & = \frac{\textit{Date of Visit 2} - \textit{Date of psoriasis diagnosis}}{365.25}
 \end{aligned}$$

- Baseline sPGA
- Baseline sPGA category: 3; 4; and 5
- Baseline sPGA category: 3; and combined 4 or 5
- Baseline PASI score
- Baseline PASI category: <20; and ≥20
- Baseline BSA (%)
- Baseline BSA category: <20%; and ≥20%
- Nail psoriasis: yes; and no

- Baseline Nail Psoriasis Severity Index (NAPSI) score
- Scalp psoriasis: yes; and no
- Baseline Psoriasis Severity Index (PSSI) score
- Palmoplantar psoriasis: yes; and no
- Baseline Palmoplantar Psoriasis Severity Index (PPASI) score
- Baseline Itch NRS score
- Baseline Itch NRS category: <4 ; and ≥ 4
- Baseline Children's Dermatology Life Quality Index (CDLQI) total score
- Baseline Dermatology Life Quality Index (DLQI) total score
- Patient's Global Assessment of Disease Severity (PatGA)
- PatGA category: 0; 1; 2; 3; 4; and 5
- Baseline Children's Depression Rating Scale, Revised (CDRS-R)
- Baseline CDRS-R category: ≤ 28 ; 29-39; and ≥ 40
- Baseline Columbia Suicide Severity Rating Scale (C-SSRS)
- Binary questions on psoriasis location
- Tanner Stage Scale

By-patient listings of demographic and baseline characteristics, respectively, for the ITT Population will be provided.

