6.11.4. Other Secondary Efficacy Analyses

There will be no adjustment for multiple comparisons for other secondary analyses.

The other secondary efficacy variables include:

- PASI 50, PASI 90, PASI 100, PASI change from baseline percent improvement

- sPGA (0)
- NAPSI change from baseline
- PSSI change from baseline
- PPASI change from baseline

The other secondary analyses for the Double-Blind Treatment Period (Period 2) will be based on the ITT Population, except (refer to [Table RHCD.6.4](#)):

- NAPSI: based on ITT Population – patients with baseline nail involvement (NAPSI baseline score >0)
- PSSI: based on ITT Population – patients with baseline scalp involvement (PSSI baseline score >0)
- PPASI: based on ITT Population – patients with baseline palmoplantar involvement (PPASI baseline score >0)
- Binary questions on psoriasis locations

The other secondary analyses are detailed in [Table RHCD.6.4](#). Comparisons of ixekizumab versus placebo at Week 12 and all other postbaseline visits will be provided.

Efficacy measures PASI 75, PASI 90, PASI 100, sPGA (0,1), and sPGA (0) at Week 24 and Week 48 will be summarized based on the ITT Population. The immunogenicity impact on efficacy is described in Section [6.14.11.2.2](#).

Protocol Addendum IIF-MC-RHCD(2)

The other secondary efficacy variables include:

- Period 2: ITT Population – Etanercept-Approved Countries
 - PASI50, PASI75, PASI90 and PASI100
 - sPGA (0,1) and sPGA (0)
- Double-Blind Randomized Withdrawal Period (Period 4): Randomized Withdrawal Population
 - Time to relapse to moderate severity (sPGA \geq 2) during the Double-Blind, Randomized Withdrawal Period
 - sPGA(0,1) and sPGA (0)
 - PASI 50, PASI 75, PASI 90 and PASI 100

The other secondary analyses are detailed in [Table RHCD.6.4](#). Analysis methods are detailed in Section [6.1.3.1](#).

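### No Period 4 efficacy analysis or specified table uses Week 60 sPGA (0 vs 1), although it sets the distance to the relapse threshold and is already recorded

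*SAP*

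**What the plan says.** SAP 6.1.2 fixes the reference point for the withdrawal period: "the baseline for efficacy and health-outcome analyses will be defined as the measure recorded at Week 0 (Visit 2". The same paragraph takes the safety baseline for that period from the last values before the Week 60 re-randomization.

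SAP 6.1.3.4 counts time to relapse from re-randomization to the first sPGA of 2 or more. It states "Treatment group comparisons will be performed using the log-rank test" and names no strata. For categorical outcomes in this period it names Fisher's exact test only.

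SAP 6.2 keeps weight at re-randomization out of the Period 4 models and does not mention sPGA at entry.

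SAP 6.8.1 applies its list of characteristics, with between-arm tests, to the withdrawal population. The list has weight measured at Visit 2 and "Baseline sPGA category: 3; 4; and 5". A Week 60 score of 0 or 1 has no category there.

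Table RHCD.6.4 places the withdrawal population in the sPGA (0,1) block whose method cell lists Fisher's exact test and logistic regression. For the addendum variables SAP 6.11.4 says "Analysis methods are detailed in Section" and points to 6.1.3.1. The model there is a "logistic regression analysis with treatment group, region, baseline sPGA score (severity of Ps), and baseline weight category".

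**The concern.** A subject who enters at sPGA 1 relapses after worsening by one grade; a subject who enters at 0 must worsen by two. Entry sPGA is therefore a plausible predictor of time to relapse. It costs nothing to obtain, because it decides who is re-randomized.

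As specified, a chance difference between arms in this score would be neither adjusted for nor shown in the balance table. That table describes disease and weight 60 weeks before the randomization it is meant to check, and before 40 to 60 weeks of ixekizumab. The covariates in the logistic model have the same age. Its region term is constant, since everyone in this population is from the EU and 6.8.1 treats the EU as one region. Read with 6.2, the model would adjust growing children for their Week 0 weight category while leaving out their weight at re-randomization.

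At stake are some precision when the effect is smaller than planned, and the ability to interpret the result if the arms of 20 differ at entry.

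**Working it through.** **1. The plan's own figure.** SAP 5.2.2 gives about 95% power for time to relapse, from a two-sided log-rank test at 0.05 with 20 subjects per arm. Its assumed rates are "20% relapse for ixekizumab; and 85% relapse for placebo".

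- Hazard ratio = ln(0.80)/ln(0.15) = 0.118.
- Expected events = 20 × 0.20 + 20 × 0.85 = 21.
- Freedman: power = Φ(√21 × (1 − 0.118)/(1 + 0.118) − 1.96) = 95.1%.

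The stated figure reproduces. Freedman's formula is conservative here: Schoenfeld's gives 99.8%, and simulation (step 4) also gives more than 99%.

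**2. Chance imbalance.** The documents do not give the share entering at sPGA 1. Assume 50%, so the count in each arm is Binomial(20, 0.5). The chance that the counts differ by 4 or more (20 points) is 0.268. With the total fixed at 20 of 40 it is 34%, and at 12 or 28 of 40 it is 30%. For 30 points or more the fixed-total figures are 11% and 8%.

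**3. What an imbalance does.** Suppose entry at 1 triples the relapse hazard (assumption) and the arms split 60% v 40%. Average relative hazards at the start are 0.4 × 1 + 0.6 × 3 = 2.2 and 0.6 × 1 + 0.4 × 3 = 1.8. Their ratio is 2.2/1.8 = 1.22, a shift of about 22% in the apparent hazard ratio.

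**4. Unstratified v stratified log-rank test, simulated.** Inputs: 20 per arm, 12 four-weekly visits, two-sided 0.05, and overall relapse by 48 weeks held at the rates shown. The prognostic hazard ratio (HR) compares entry at 1 with entry at 0. The table assumes half the subjects enter at sPGA 1.

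| Relapse, ixekizumab v placebo | HR 2 | HR 3 | HR 4 |
|---|---|---|---|
| 30% v 70%, unstratified | 76.0% | 77.0% | 77.6% |
| 30% v 70%, stratified | 77.3% | 82.5% | 86.6% |
| 40% v 80%, unstratified | 80.0% | 81.4% | 82.6% |
| 40% v 80%, stratified | 81.9% | 87.8% | 92.3% |

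- The gain runs from 1.3 points (77.3 − 76.0) to 9.7 points (92.3 − 82.6).
- If entry sPGA is not prognostic (HR 1), stratifying loses about 1.5 to 2 points at these effect sizes.
- At the planned 20% v 85%, with shares of 30% to 70% and HRs of 1 to 5, power is 99.5% to 99.9% unstratified and 99.6% to 100% stratified.
- Overall type I error is close to 5% for both tests (5.1% to 5.2% in the larger simulation).
- Among simulated null trials with an imbalance of 30 points or more (about 8% of them), the unstratified test rejects in about 8% at HR 2 and 10% to 13% at HR 3. The stratified test stays near 5.5%. At the planned effect, power in such trials is still 98.8% or more.

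**The case against.** The strongest reply is that the unstratified test is sound. Re-randomization protects its type I error, and at the planned effect stratifying changes nothing of consequence. Even a 22% shift would move the planned hazard ratio only from 0.118 to 0.118 × 1.22 = 0.144. The gains in power need relapse rates that the plan does not assume, together with an assumed share and assumed prognostic strength. With about 10 subjects per arm per stratum, stratification is partly a matter of choice, and 6.2 suggests that leaving Period 4 unadjusted was deliberate. The endpoints are other secondary, without multiplicity control. All of this stands, and it limits the size of the point.

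A reader might infer that the Week 0 baseline causes the problem, or that it is an error. The documents do not support that. Time to relapse starts at Week 60 and ends at an absolute score, and sPGA (0,1) is also absolute, so neither uses the Week 0 value. Changing 6.1.2 alone would leave the log-rank test as it is. Week 0 is also the right reference for PASI 50/75/90/100, which are percent improvements from pre-treatment disease. A reader might also infer a biased comparison or a likely imbalance; the test is unbiased over re-randomization, and 27% is not likely.

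The logistic regression reaches Period 4 only through a method cell shared with Period 2 rows and a general cross-reference to a Period 2 section. It may not be intended, but that is a reason to reconcile the text. Finally, sPGA (0) is a listed Period 4 variable in 6.11.4, so a Week 60 row could show the entry split. The SAP does not specify one.

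**Conclusion.** The point holds as a low-cost improvement in precision and in robustness to chance imbalance, plus a reconciliation of text. It does not correct a bias and does not affect the stated power.

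Three parts need no assumption: the log-rank test has no strata; the baseline table for the withdrawal population describes Week 0; and 6.1.3.4 disagrees with Table RHCD.6.4 and 6.11.4 on whether a logistic regression applies in Period 4, the model pointed to having Week 0 covariates and a one-level region term.

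The size depends on assumptions. With half the subjects at sPGA 1, a 20-point or larger imbalance has a 27% chance. With a prognostic hazard ratio of 2 to 4 and a smaller treatment effect than planned, stratifying gains about 1 to 10 points of power. At 20% v 85% the effect on power is negligible either way.

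**What to change.** - **SAP 6.1.2:** keep Week 0 as the Period 4 reference for PASI percent improvement. Add that covariates and the description of the withdrawal population use the last value before re-randomization at Week 60.
- **SAP 6.8.1:** for the withdrawal population, tabulate Week 60 sPGA (0 vs 1), PASI, weight and Period 2 arm by re-randomized arm.
- **SAP 6.1.3.4:** stratify the time-to-relapse log-rank test by Week 60 sPGA (0 vs 1). Because section 10.3.1 of the protocol addendum also names the log-rank test, the acceptable minimum is to keep the unstratified test as the main analysis and prespecify the stratified one as a sensitivity analysis.
- **Table RHCD.6.4, 6.11.4, 6.1.3.4 and 6.2:** state whether a Period 4 logistic regression is intended. If it is kept, use Week 60 sPGA, drop region, and settle which weight, if any, enters the model.

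The cost is SAP wording and reprogramming with data already collected, and about 1.5 to 2 points of power at smaller effects if entry sPGA is not prognostic. The change should be dated and made before Period 4 results by arm are seen. The lock at the end of Period 2 described in SAP 6.17 includes any Period 4 data collected by its cutoff, so the amendment should record what had been unblinded by then.
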